[Part 2 of 3 of the document. The other parts are not shown.]

The last dose of study drug will be administered the day before Visit 9. At study Visit 9, the patient has the option to enroll in an open-label extension study (A4250-008) should they meet the required entry criteria. If the patient is continuing into Study A4250-008 this will be the last visit in this study and the first visit in Study A4250-008. Visit 9/EOT should also be performed at the time patients are prematurely withdrawn from the study.

Clinic Visit 10 will take place 28 days after Visit 9 for all patients not continuing into Study A4250-008.

**Figure 1 Study Design**

T: telephone contact; V: study visit

## End of Study

The end of the study is defined as follows:

- End of study in one country: last patient last visit (LPLV) and sites are closed
- End of study globally: LPLV globally and all sites closed

## 7.1.2 Schedule of Assessments

The schedule of assessments is presented in [Table 1](#). For information on blood volumes, please see [Appendix 7](#).

**Table 1 Schedule of Assessments**

Study Activity	Screening Period		Treatment Period								Follow-Up
			Random-ization	Phone Contact	4 weeks	8 weeks	12 weeks	18 weeks	22 weeks	24 weeks	
Study Days	-56 – (-35) ±2	-28 – (-7) ±2	0	14 ±3	28 ±3	56±3	84±3	126 ±3	154 ±3	168 ±3	196 ±3
Visits	Clinic Visit 1	Clinic Visit 2	Clinic Visit 3	n/a	Clinic Visit 4	Clinic Visit 5	Clinic Visit 6	Clinic Visit 7	Clinic Visit 8	Clinic Visit 9/EOT a	Clinic Visit 10 b
Informed consent c	X										
Inclusion/exclusion criteria	X		X								
Demographics	X										
Concomitant medication d	X	X	X	X	X	X	X	X	X	X	X
Medical and surgical history	X		X								
Physical examination including voluntary photography	X		X				X			X	
Skin examination	X		X		X		X			X	X
Vital signs e	X	X	X		X	X	X	X	X	X	X
eDiary: itching, scratching, and sleep scores f	Daily diary entry										
Clinical chemistry g	X		X		X	X	X	X		X	X
Hematology g			X		X	X	X	X		X	X
Urinalysis g		X					X			X	
Serum bile acids h	X	X	X		X	X	X	X	X	X	X

Study Activity	Screening Period		Treatment Period								Follow-Up
			Randomization	Phone Contact	4 weeks	8 weeks	12 weeks	18 weeks	22 weeks	24 weeks	
Study Days	-56 – (-35) ±2	-28 – (-7) ±2	0	14 ±3	28 ±3	56±3	84±3	126 ±3	154 ±3	168 ±3	196 ±3
Visits	Clinic Visit 1	Clinic Visit 2	Clinic Visit 3	n/a	Clinic Visit 4	Clinic Visit 5	Clinic Visit 6	Clinic Visit 7	Clinic Visit 8	Clinic Visit 9/EOT a	Clinic Visit 10 b
INR		X			X		X		X		X
Autotaxin i			X		X					X	
p-C4 i			X		X					X	
AFP			X							X	
Vitamins A & E h		X					X			X	
25-hydroxy vitamin D			X				X			X	
Blood sample for A4250 PK i					X					X	
Abdominal Ultrasound			X							X	
Fibroscan ® (where available)			X							X	
QoL questionnaire (PedsQL)			X							X	
Patient/Caregiver/Clinician Global Impression of Change					X		X			X	
Patient/Caregiver/Clinician Global Impression of Symptoms			X		X		X			X	
Pregnancy test j	X j	X	X		X	X	X	X	X	X j	X

Study Activity	Screening Period		Treatment Period								Follow-Up
			Randomization	Phone Contact	4 weeks	8 weeks	12 weeks	18 weeks	22 weeks	24 weeks	
Study Days	-56 – (-35) ±2	-28 – (-7) ±2	0	14 ±3	28 ±3	56±3	84±3	126 ±3	154 ±3	168 ±3	196 ±3
Visits	Clinic Visit 1	Clinic Visit 2	Clinic Visit 3	n/a	Clinic Visit 4	Clinic Visit 5	Clinic Visit 6	Clinic Visit 7	Clinic Visit 8	Clinic Visit 9/EOT a	Clinic Visit 10 b
Study drug dispensed k			X		X	X	X	X	X		
Adverse events l	Continuous collection										
Study drug compliance					X	X	X	X	X	X	

AFP: alfa-fetoprotein; BMI: body mass index; eCRF: electronic case report form; eDiary: electronic diary; EOT: End of Treatment; ICF: informed consent form; INR: international normalized ratio; p-C4: plasma 7 $\alpha$  Hydroxy 4-cholesten-3-one; PedsQL: Pediatric Quality of Life Inventory; PK: pharmacokinetic; QoL: quality of life; RR: respiratory rate; SAE: serious adverse event; s-BA: serum bile acid.

- a Must also be performed at the time a patient is prematurely withdrawn from the study. This visit is the same as Visit 1 in the extension protocol (Study A4250-008).
- b Assessments must be performed 28 days following the final dose of study drug. This visit is omitted if patients are entering Study A4250-008.
- c The ICF (and assent) must be signed before any study procedures are performed.
- d Past (within 1 month prior to Visit 1) and current medication will be documented in the eCRF.
- e Includes blood pressure, pulse, RR, temperature, height (or length depending on age), and body weight (using a certified weight scale). BMI will be calculated.
- f Includes training on use of the device at Screening (Visit 1) and review of patient daily entries during 14 days prior to Clinic Visit 3 to determine eligibility.
- g See [Table 3](#) for detailed parameters.
- h Patients will fast (water intake only is permissible) for at least 4 hours prior to the collection of samples for s-BA and vitamin A. Exceptions can be made for infants, less than 12 months of age, if unable to fast for the full 4 hours. All s-BA results during the treatment period and follow-up will be blinded.
- i Samples will not be collected for patients  $\leq 10$  kg. In the event of an SAE, a PK sample should be collected as close to the onset of the event as possible.
- j For girls who have reached menarche. Serum test at Visit 1; urine test at other visits. A serum pregnancy test will also be conducted at Visit 9 for patients entering Study A4250-008. If a urine pregnancy test is positive, a serum pregnancy test should be performed to confirm the pregnancy.
- k Study drug to be taken once daily on Day 1 through Day 167 as described in [Section 8.2](#).

Study Activity	Screening Period		Treatment Period								Follow-Up
			Randomization	Phone Contact	4 weeks	8 weeks	12 weeks	18 weeks	22 weeks	24 weeks	
Study Days	-56 – (-35) ±2	-28 – (-7) ±2	0	14 ±3	28 ±3	56±3	84±3	126 ±3	154 ±3	168 ±3	196 ±3
Visits	Clinic Visit 1	Clinic Visit 2	Clinic Visit 3	n/a	Clinic Visit 4	Clinic Visit 5	Clinic Visit 6	Clinic Visit 7	Clinic Visit 8	Clinic Visit 9/EOT a	Clinic Visit 10 b

1 Adverse event information will be collected from the time of signing of the ICF to study discontinuation.

### 7.1.3 Study Procedures and Assessments

#### 7.1.3.1 Screening Period (Days -56 to 0)

##### Day -56 to Day -35/Clinic Visit 1

Patients will undergo a Screening Visit up to 56 days prior to the planned first day of study treatment. Screening procedures and assessments are as follows:

- Obtain written informed consent
- Assess inclusion/exclusion criteria ([Section 7.2](#))
- Record demographics (age, full date of birth, gender, race, and ethnicity)
- Document concomitant medications
- Medical and surgical history (date of diagnosis of PFIC Types 1 or 2, prior investigational medications for PFIC, historical liver function test [LFT] values, any surgery performed, any other diagnosis, and historical liver biopsy data)
- Collect, if available, past confirmatory clinical genetic laboratory report for PFIC-1/PFIC-2 and send to central reader for review. If a historical report is equivocal, unavailable, or unobtainable, a blood sample for clinical genetic testing will be collected to determine eligibility
- Physical examination, including voluntary photography ([Section 10.2.5](#))
- Skin examination ([Section 10.2.5](#))
- Vital signs ([Section 10.2.6](#))
- eDiary training and compliance requirements; caregivers and, if applicable, patients begin daily recording of pruritus using the eDiary ([Appendix 2](#))
- Clinical chemistry ([Section 10.2.1](#))
- s-BA ([Section 9.2.1](#))
- Serum pregnancy test for girls who have reached menarche. Please see [Appendix 6](#) for contraceptive requirements
- AE monitoring

##### Day -28 to Day -7/Clinic Visit 2

A second Screening Visit will be performed. Screening procedures and assessments are as follows:

- Review concomitant medications
- Vital signs ([Section 10.2.6](#))
- Albireo PRO/ObsRO eDiary review for compliance

- Urinalysis ([Section 10.2.1](#))
- s-BA ([Section 9.2.1](#))
- International normalized ratio (INR)
- Vitamins A and E
- Urine pregnancy test for girls of who have reached menarche
- AE monitoring

### **7.1.3.2 Treatment Period (Day 0 to Day 168)**

#### **Study Day 0/Clinic Visit 3 (Randomization)**

At the randomization visit, the following assessments will be conducted:

- Review inclusion/exclusion criteria ([Section 7.2](#))
- Review concomitant medications, medical and surgical history
- Physical examination, including voluntary photography ([Section 10.2.5](#))
- Skin examination ([Section 10.2.5](#))
- Vital signs ([Section 10.2.6](#))
- Albireo PRO/ObsRO eDiary review for compliance and entrance criteria requirement (see Inclusion Criteria 4, [Section 7.2.1](#))
- Clinical chemistry and hematology ([Section 10.2.1](#))
- s-BA ([Section 9.2.1](#))
- Autotaxin and p-C4 (samples will not be taken for patients  $\leq 10$  kg)
- 25-hydroxy vitamin D
- Alfa-fetoprotein (AFP)
- Abdominal ultrasound ([Section 10.2.7](#))
- Fibroscan®, where available ([Section 9.2.7](#))
- Administer QoL (Pediatric Quality of Life Inventory [PedsQL]) questionnaire
- Patient/caregiver/clinician complete the patient global impression of symptoms (PGIS)
- Urine pregnancy test for girls who have reached menarche
- AE monitoring
- Study drug is dispensed and patients are instructed to administer daily from Day 1

#### **Study Day 14 (Telephone Contact)**

A study nurse will contact the patient/caregiver by telephone for monitoring of the following:

- Review concomitant medications
- Albireo PRO/ObsRO eDiary review for compliance
- AEs

#### **Study Day 28 and Day 84/Clinic Visits 4 and 6**

The following procedures and assessments will be performed:

- Review of concomitant medications
- Physical examination, including voluntary photography (at Clinic Visit 6 only; [Section 10.2.5](#))
- Skin examination ([Section 10.2.5](#))
- Vital signs ([Section 10.2.6](#))
- Albireo PRO/ObsRO eDiary review for compliance
- Clinical chemistry and hematology ([Section 10.2.1](#))
- Urinalysis (at Clinic Visit 6 only; [Section 10.2.1](#))
- s-BA ([Section 9.2.1](#))
- INR
- Autotaxin, p-C4, and A4250 pharmacokinetic (PK) assessment (at Clinic Visit 4 only; samples will not be taken for patients  $\leq 10$  kg)
- Vitamins A and E, and 25-hydroxy vitamin D (at Clinic Visit 6 only)
- Patient/caregiver/clinician complete the patient global impression of change (PGIC) and PGIS
- Urine pregnancy test for girls who have reached menarche
- AE monitoring
- Evaluation of study drug compliance
- Study drug is dispensed

#### **Study Day 56 and Day 126/Clinic Visits 5 and 7**

The following procedures and assessments will be performed:

- Review of concomitant medications
- Vital signs ([Section 10.2.6](#))
- Albireo PRO/ObsRO eDiary review for compliance
- Clinical chemistry and hematology ([Section 10.2.1](#))

- s-BA ([Section 9.2.1](#))
- Urine pregnancy test for girls who have reached menarche
- AE monitoring
- Evaluation of study drug compliance
- Study drug is dispensed

#### **Study Day 154/Clinic Visit 8**

The following procedures and assessments will be performed:

- Review of concomitant medications
- Vital signs ([Section 10.2.6](#))
- Albireo PRO/ObsRO eDiary review for compliance
- s-BA ([Section 9.2.1](#))
- INR
- Urine pregnancy test for girls who have reached menarche
- AE monitoring
- Evaluation of study drug compliance
- Study drug is dispensed

#### **Study Day 168/Clinic Visit 9/EOT**

The last dose of study drug is taken in the morning the day before Clinic Visit 9, and the following procedures and assessments will be performed (also performed at the time a patient prematurely withdraws):

- Review of concomitant medications
- Physical examination, including voluntary photography ([Section 10.2.5](#))
- Skin examination ([Section 10.2.5](#))
- Vital signs ([Section 10.2.6](#))
- Albireo PRO/ObsRO eDiary review for compliance
- Clinical chemistry, hematology, and urinalysis ([Section 10.2.1](#))
- s-BA ([Section 9.2.1](#))
- Autotaxin, p-C4, and A4250 PK assessment (samples will not be taken for patients  $\leq 10$  kg)
- AFP

- Vitamins A, E, and 25-hydroxy vitamin D
- Abdominal ultrasound ([Section 10.2.7](#))
- Fibroscan®, where available ([Section 9.2.7](#))
- Administer PedsQL questionnaire
- Patient/caregiver/clinician complete the PGIC and PGIS
- Urine pregnancy test for girls who have reached menarche, or serum pregnancy test for girls continuing to study A4250-008
- AE monitoring
- Evaluation of study drug compliance

### **7.1.3.3 Follow-Up Period**

#### **Study Day 196/Clinic Visit 10**

All patients not continuing into Study A4250-008 will return to the study site 28 days after Clinic Visit 9 or the last dose of study drug for the following assessments:

- Review of concomitant medications
- Skin examination ([Section 10.2.5](#))
- Vital signs ([Section 10.2.6](#))
- Albireo PRO/ObsRO eDiary review for compliance
- Clinical chemistry and hematology ([Section 10.2.1](#))
- s-BA ([Section 9.2.1](#))
- INR
- Urine pregnancy test for girls who have reached menarche
- AE monitoring

## **7.2 Study Population**

A total of approximately 60 patients with a clinical diagnosis of PFIC Type 1 or 2 that have been genetically confirmed will be randomized. The study will target 15% of enrolled patients to be PFIC-1 patients. If enrollment of all PFIC-2 patients is completed and the 15% enrollment of PFIC-1 patients has not yet been achieved, then enrollment of PFIC-2 patients will continue in order to reach the total study target enrollment.

An attempt will be made to randomize a minimum of 10 patients from each age category (6 months to 5 years, 6 to 12 years, and 13 to ≤18 years).

A maximum of 5 patients that were treated in Study A4250-003 will be allowed to participate in this study.

### 7.2.1 Inclusion Criteria

1. A male or female patient, with clinical diagnosis of PFIC Type 1 or 2, between the ages of  $\geq 6$  months and  $\leq 18$  years at Visit 1 with a body weight above 5 kg
2. Patient must have clinical genetic confirmation of PFIC-1 or PFIC-2 through identification of biallelic pathogenic variants in either the *ATP8B1* or *ABCB11* genes
3. Patient must have elevated s-BA concentration, specifically measured to be  $\geq 100$   $\mu\text{mol/L}$ , taken as the average of 2 samples at least 7 days apart (Visits 1 and 2) prior to randomization
4. Patient must have history of significant pruritus and a caregiver-reported observed scratching in the eDiary average of  $\geq 2$  (on 0 to 4 scale) in the 2 weeks prior to randomization
5. Patient and/or legal guardian must sign informed consent (and assent) as appropriate. Patients who turn 18 years of age (or legal age per country) during the study will be required to re-consent in order to remain in the study
6. Patients will be expected to have a consistent caregiver for the duration of the study
7. Caregivers and age-appropriate patients ( $\geq 8$  years of age) must be willing and able to use an eDiary device as required by the study

### 7.2.2 Exclusion Criteria

1. Patient with pathologic variations of the *ABCB11* gene that predict complete absence of the BSEP protein
2. Patient with past medical history or ongoing presence of other types of liver disease including, but not limited to, the following:
  - a) Biliary atresia of any kind
  - b) Benign recurrent intrahepatic cholestasis, indicated by any history of normal s-BAs
  - c) Suspected or proven liver cancer or metastasis to the liver on imaging studies
  - d) Histopathology on liver biopsy is suggestive of alternate non-PFIC related etiology of cholestasis
3. Patient with a past medical history or ongoing presence of any other disease or condition known to interfere with the absorption, distribution, metabolism (specifically bile acid metabolism), or excretion of drugs in the intestine, including but not limited to, inflammatory bowel disease
4. Patient with past medical history or ongoing chronic (i.e.,  $>3$  months) diarrhea requiring intravenous fluid or nutritional intervention for treatment of the diarrhea and/or its sequelae

5. Patient has a confirmed past diagnosis of infection with human immunodeficiency virus or other present and active, clinically significant, acute, or chronic infection, or past medical history of any major episode of infection requiring hospitalization or treatment with parenteral anti-infective treatment within 4 weeks of treatment start (study Day 1) or completion of oral anti-infective treatment within 2 weeks prior to start of Screening Period
6. Any patient with suspected or confirmed cancers except for basal cell carcinoma, and non-liver cancers treated at least 5 years prior to Screening with no evidence of recurrence
7. Patient with a past medical history of chronic kidney disease with an impaired renal function and a glomerular filtration rate  $<70$  mL/min/1.73 m^2
8. Patient with surgical history of disruption of the enterohepatic circulation excluding those who have undergone a successful reversal procedure that has permanently restored flow of bile acids from the liver to the duodenum
9. Patient has had a liver transplant or a liver transplant is planned within 6 months of randomization
10. Decompensated liver disease, coagulopathy, history or presence of clinically significant ascites, variceal hemorrhage, and/or encephalopathy
11. INR  $>1.4$  (the patient may be treated with Vitamin K intravenously, and if INR is  $\leq 1.4$  at resampling the patient may be randomized)
12. Serum ALT  $>10 \times$  upper limit of normal (ULN) at Screening
13. Serum ALT  $>15 \times$  ULN at any time point during the last 6 months unless an alternate etiology was confirmed for the elevation
14. Total bilirubin  $>5 \times$  ULN at Screening
15. Patient suffers from uncontrolled, recalcitrant pruritic condition other than PFIC. Examples include, but not limited to, refractory atopic dermatitis or other primary pruritic skin diseases
16. Any patient who is pregnant or lactating or who is planning to become pregnant within 24 weeks of randomization
17. Sexually active males and females who are not using a reliable contraceptive method with  $\leq 1\%$  failure rate (such as hormonal contraception, intrauterine device, or complete abstinence) throughout the duration of the study and 90 days thereafter (from signed informed consent through 90 days after last dose of study drug). See [Appendix 6](#) for further details

18. Patient with a past medical history of alcohol or substance abuse will be excluded. Patient must agree to refrain from illicit drug and alcohol use during the study
19. Administration of bile acid or lipid binding resins and medications that slow GI motility (Refer to [Appendix 1](#) – Concomitant Medications Guidelines)
20. Patient has had investigational exposure to a drug, biologic agent, or medical device within 30 days prior to Screening, or 5 half-lives of the study agent, whichever is longer
21. Patient who has been previously treated with an IBAT inhibitor whose pruritus has not responded to treatment
22. Any other conditions or abnormalities which, in the opinion of the investigator or Medical Monitor, may compromise the safety of the patient, or interfere with the patient participating in or completing the study

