- Proportion of individual PM assessments meeting the definition of a positive pruritus assessment at the subject level from Weeks 0-4, Weeks 0-8, Weeks 0-12, Weeks 0-18, Weeks 0-24, respectively, or the proportion of positive pruritus assessments at each 4-week interval.
- Number of patients undergoing biliary diversion surgery or being listed for liver transplantation

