### **11.1 Sample Size and Power**

For the EU and RoW, the primary analysis will relate to the serum bile acid responder endpoint. For the US, the primary analysis will relate to the pruritus endpoint. For each primary endpoint, a pooled analysis for the closed testing procedure will be applied to control the 1-sided overall type I error rate for two treatment comparisons vs. the placebo at the 0.025 level (Kane et al, 2015, Lehmacher et al, 1991, and Marcus et al, 1976). The study will enroll 60 to 70 patients in order to obtain at least 20 evaluable patients in each arm. For each primary endpoint, simulations with 5000 iterations using 20 patients per arm were conducted to estimate the power after multiplicity adjustment, resulting in a standard error of <0.7% for each estimated power.

Based on the Phase 2 A4250-003 study data both dose groups are predicted to have similar treatment effects for both serum bile acids and pruritus. For serum bile acids, simulated proportions were analyzed using the CMH test to generate the following 1-sided p-values: both A4250 arms pooled vs. placebo, low dose vs. placebo, and high dose vs. placebo. Assuming 60% responders in the A4250 arms and 10% responders in the placebo arm, the power to claim significance for a particular A4250 arm after multiplicity adjustment is approximately 94%. The power to claim significance for at least one arm or both arms are approximately 99% and 91%, respectively.

For the proportion of positive pruritus assessments at the subject level in pruritus scores, simulated proportions were analyzed using ANCOVA to generate the following 1-sided p-values: both A4250 arms pooled vs. placebo, low dose vs. placebo, and high dose vs. placebo. With an effect size of 1.0526, the simulated power to claim significance for a particular arm after multiplicity adjustment is approximately 89%. The probability to claim significance for at least one arm or both arms are approximately 95% and 83%, respectively.

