#### **11.2.2.2 Missing Data**

In the primary analysis of the pruritus endpoint, all intermittently missing assessments will be classified as negative pruritus assessments. Similarly, all planned assessments after the intercurrent events (premature treatment discontinuation, death or initiation of rescue treatments such as biliary diversion surgery or liver transplantation) will be counted as negative pruritus assessments. However, as described above, all 336 assessments planned over the 24-week treatment period will be included in the denominator of the endpoint definition.

In the primary analysis of fasting bile acid responder endpoint, dropouts and patients with a missing average at the end of the treatment will be treated as non-responders. Patients in need of surgical rescue, i.e. biliary diversion and listing for liver transplant will be classified as non-responders. Continued collection of efficacy data for patients who discontinue treatment will be made as far as possible.

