#### **11.2.2.5 Evaluation of Primary Efficacy Variables**

For EU and RoW, the primary responder endpoint based on change in fasting bile acids will be analyzed in terms of the proportion of patients achieving the event of interest. Patients in need of surgical rescue, i.e. biliary diversion and listing for liver transplant, will be classified as non-responders. Dropouts will be treated as non-responders.

CMH stratified by PFIC class and age class will be performed to compare the proportion in fasting bile acid responders at the end of treatment (Week 22 and 24) in the two A4250 dose groups to the placebo group. To ascertain that all data are used in the CMH analysis, neighboring strata will be pooled if all subjects in a stratum have the same response. The proportion together with corresponding 95% CI, odds ratio and corresponding 95% Clopper-Pearson exact CI and p-value for the CMH test will be presented

Logistic regression will be performed as a supportive analysis to compare the proportion in fasting bile acid responders at the end of treatment (Week 22 and 24) in the two A4250 dose groups to the placebo group. The model will include treatment arm, baseline value, and randomization stratification factors, i.e. PFIC class and age class. Baseline value will be calculated as the average of serum bile acid values at randomization and the previous visit (Clinic Visit 2).

In the US, for the primary efficacy variable of the proportion of positive pruritus assessments at the subject level over the 24-week treatment period, ANCOVA will be used to analyze the pruritus endpoint. The model will include treatment arm, the averaged AM and PM baseline pruritus scores, and randomization stratification factors, i.e. PFIC class and age class. LS mean(SE) by treatment arm and LS mean difference (SE), 95% confidence intervals, and p-values (where applicable) between treatments (120 µg/kg/day and 40 µg/kg/day, respectively) vs. placebo will be provided. If there are concerns on model assumptions, i.e. normality and homogeneity of variances, a non-parametric ANCOVA based on the rank scores can be used. LS mean/SE on the outcome by treatment arm and LS mean difference/SE between active dose and placebo will be provided.

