### **11.2.2.6 Evaluation of Secondary and Exploratory Efficacy Variables**

The change in the secondary endpoints such as serum bile acids, total bilirubin, ALT, growth, Albireo PRO and ObsRO sleep parameters, and patient-reported itch severity will be summarized by visit using descriptive statistics. Change in growth (weight for age and BMI for age) will also be displayed using graphical presentations.

Proportion of responders at Weeks 12 and 24 based on the PRO/ObsRO instruments estimated from both distribution and anchor-based approaches will be analyzed using the same model as specified for the primary analysis for EU and RoW.

Proportion of individual assessments meeting the definition of a positive pruritus assessment at the subject level from Weeks 0-4, Weeks 0-8, Weeks 0-12, Weeks 0-18, Weeks 0-24, respectively, or the proportion of positive pruritus assessments at each 4-week interval over the 24-week treatment period for AM or PM, respectively will be analyzed using the same model as specified for the primary analysis for US.

Undergoing biliary diversion surgery and/or listed for liver transplant, all-cause mortality, and liver decompensation events will mainly be analyzed by using descriptive statistics. Kaplan-Meier curves will be used when appropriate for time to event data.

Comparisons of the change from baseline at Week 24 in PedsQL between the treatment groups will be conducted using ANCOVA. The model will include terms for baseline, PFIC class, age class, and treatment.

Other exploratory variables (Global Symptom Relief, biochemical markers and measures of bile acid synthesis, additional Albireo PRO and ObsRO sleep parameters, PELD/MELD score, APRI score, and Fib-4 score) will be analyzed descriptively for categorical and continuous data, as applicable. For continuous data, the change from baseline will be analyzed in addition to the actual visit values. For categorical data, shift tables or frequency and percentages of patients will be presented as appropriate. Additional details on secondary and exploratory efficacy variables and subgroup analyses by age class (6 months to 5 years, 6 to 12 years, and 13 to  $\leq 18$  years) will be specified in the SAP.

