#### **7.2.2 Exclusion Criteria**

1. Patient with pathologic variations of the *ABCB11* gene that predict complete absence of the BSEP protein
2. Patient with past medical history or ongoing presence of other types of liver disease including, but not limited to, the following:
  - a) Biliary atresia of any kind
  - b) Benign recurrent intrahepatic cholestasis, indicated by any history of normal s-BAs
  - c) Suspected or proven liver cancer or metastasis to the liver on imaging studies
  - d) Histopathology on liver biopsy is suggestive of alternate non-PFIC related etiology of cholestasis
3. Patient with a past medical history or ongoing presence of any other disease or condition known to interfere with the absorption, distribution, metabolism (specifically bile acid metabolism), or excretion of drugs in the intestine, including but not limited to, inflammatory bowel disease
4. Patient with past medical history or ongoing chronic (i.e.,  $>3$  months) diarrhea requiring intravenous fluid or nutritional intervention for treatment of the diarrhea and/or its sequelae
5. Patient has a confirmed past diagnosis of infection with human immunodeficiency virus or other present and active, clinically significant, acute, or chronic infection, or past medical history of any major episode of infection requiring hospitalization or treatment with parenteral anti-infective treatment within 4 weeks of treatment start (study Day 1) or

completion of oral anti-infective treatment within 2 weeks prior to start of Screening Period

6. Any patient with suspected or confirmed cancers except for basal cell carcinoma, and non-liver cancers treated at least 5 years prior to Screening with no evidence of recurrence
7. Patient with a past medical history of chronic kidney disease with an impaired renal function and a glomerular filtration rate  $<70 \text{ mL}/\text{min}/1.73 \text{ m}^2$
8. Patient with surgical history of disruption of the enterohepatic circulation excluding those who have undergone a successful reversal procedure that has permanently restored flow of bile acids from the liver to the duodenum
9. Patient has had a liver transplant or listed for liver transplant, excluding those who have been listed for transplant for pruritus who have since been removed from the transplant list
10. Decompensated liver disease, coagulopathy, history or presence of clinically significant ascites, variceal hemorrhage, and/or encephalopathy

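### Transplant listing counts as s-BA non-response and as a surgical event with no requirement that it be new, although exclusion 9 does not bar a child already listed at entry

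*Protocol*

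**What the plan says.** Exclusion 9 in the current Protocol 7.2.2 reads: "Patient has had a liver transplant or a liver transplant is planned within 6 months of randomization". It does not mention listing.

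For the s-BA responder endpoint, 11.2.2.2 states: "Patients in need of surgical rescue, i.e. biliary diversion and listing for liver transplant will be classified as non-responders". Section 11.2.2.5 repeats the rule almost word for word. Neither place says when the listing must occur.

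The secondary endpoint in 9.1.2 is "Number of patients undergoing biliary diversion surgery or being listed for liver transplantation". Section 11.2.2.6 analyses it mainly descriptively, with Kaplan-Meier curves where appropriate.

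The pruritus rule, also in 11.2.2.2, is timed. It scores as negative the assessments planned after an intercurrent event, and among those events it names "initiation of rescue treatments such as biliary diversion surgery or liver transplantation". Listing is not among them.

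The document also contains superseded versions, which serve here only as context. In the version dated 10 May 2018, exclusion 9 read "Patient has had a liver transplant or listed for liver transplant, excluding those who have been listed for transplant for pruritus" and went on to require that such patients had since been removed from the list. The s-BA rule in that version covered biliary diversion only, and applied only after the diversion.

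**The concern.** Three rules meet on the same child. Exclusion 9 lets in a listed child whose transplant is not planned within 6 months. The s-BA rule scores listing as non-response. The surgical endpoint counts listing as an event. With no start date attached to listing, a child on the list before Day 1 can be scored a failure on the EU/RoW primary endpoint however far the s-BA falls, and can also be counted as needing surgery under a treatment not yet begun.

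The rules are fixed in the protocol, so an analyst who ignores listing at entry departs from their literal words, while one who applies them scores a baseline characteristic as an outcome. Two analysts could classify the same child differently on a primary endpoint in a trial of about 60 patients. The s-BA responder endpoint is also the US secondary, and the surgical endpoint would mix status at entry with events on study.

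**Working it through.** **Side by side.** The pruritus rule has an explicit clock (assessments after the event) and names transplantation. The s-BA rule, in the same section, has no clock and names listing. The surgical endpoint has no clock and names listing. The ambiguity therefore lies in the s-BA rule and the surgical endpoint only.

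**Inputs from Protocol 11.1.** Responder rates are 60% on A4250 and 10% on placebo, with 20 patients per arm. The closed test is to "control the 1-sided overall type I error rate for two treatment comparisons vs. the placebo at the 0.025 level". Stated power is about 94% for a particular arm, 99% for at least one arm and 91% for both.

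**Reproducing the stated figure.** Normal approximation with pooled variance under the null:

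power = Φ{ [ (p1 − p0) − 1.96·√(2·p̄(1−p̄)/n) ] / √( [p1(1−p1) + p0(1−p0)]/n ) }

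With p1 = 0.60, p0 = 0.10, p̄ = 0.35 and n = 20, this is Φ{ (0.50 − 1.96 × 0.1508) / 0.1285 } = Φ(1.59) = 94.4%.

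A simulation of 5000 trials tested pooled active against placebo and then each dose, each at one-sided 0.025, with a single stratum and no continuity correction. It gave 94.9% for one arm, 98.2% for at least one and 91.5% for both. The plan's power figure is not in dispute.

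**Adding the literal listing rule.** Let q be the share of each arm listed at entry and scored non-responder. Assume these children would otherwise respond at the same rate as the rest. The rates become 0.60(1−q) and 0.10(1−q). The protocol gives no value for q, so a range is shown.

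| q (assumed) | Active | Placebo | Difference (points) | One arm, formula | One arm, simulated | Both arms, simulated |
|---|---|---|---|---|---|---|
| 0 | 60% | 10% | 50 | 94.4% | 94.9% | 91.5% |
| 5% | 57% | 9.5% | 47.5 | 92.3% | 92.8% | 88.2% |
| 10% | 54% | 9% | 45 | 89.6% | 90.8% | 84.8% |
| 20% | 48% | 8% | 40 | 83.1% | 85.0% | 76.9% |
| 30% | 42% | 7% | 35 | 74.9% | 76.7% | 66.4% |

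The simulated one-arm column is the low dose; the high dose agrees within one point. A six-stratum CMH test (15% PFIC-1 as targeted, ages assumed in equal thirds) starts lower and falls similarly: one-arm power is 90.8% at q = 0, 89.4% at 5% and 85.8% at 10%.

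**One patient.** A listed child who would otherwise respond moves an arm's rate by 1/20 = 5 points.

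**Surgical endpoint.** On the literal reading, 60 × 0.05 = 3 to 60 × 0.10 = 6 patients would be counted as listed without any event on study.

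**If patients listed at entry are scored on their s-BA values,** q has no effect through this rule and the first row of the table stands.

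**The case against.** The strongest reply is that the harmful reading is not the natural one. Rescue means something that happens after treatment starts. Being listed is worded as an event, and the Kaplan-Meier provision in 11.2.2.6 needs an event time that a listing before Day 0 does not have. This has force and makes the remedy a clarification. It does not remove the point, because the sentence equates surgical rescue with listing and puts no date on it, while the neighbouring pruritus rule is dated.

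A second reply is that the group may be small or empty. The protocol does not say whether being listed counts as a transplant planned within 6 months, exclusions 10 and 14 remove many advanced cases, and exclusion 22 leaves discretion. That is fair, and it is why q is shown only as an assumption.

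A third is that dating events is a matter for the SAP, which was not at hand. Section 11.2.2.5 leaves to the SAP the sensitivity analyses for intercurrent events, but it fixes the responder classification itself.

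A reader comparing versions might infer that eligibility was loosened and the efficacy rules were left behind. For the s-BA rule the documents show otherwise: the 10 May 2018 rule covered diversion only and was timed, and the current text added listing and dropped the timing. Only the wording of the surgical endpoint carried over. A difference from superseded text is in any case not an error; the point rests on the current sections alone.

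**Conclusion.** The current text leaves open whether a patient listed before the first dose is an s-BA non-responder and a surgical event, and its literal words say yes. The consequence is modest: for an assumed 5 to 10% listed at entry, one-arm power is about 93 to 91% against the stated 94%, and both-arm power about 88 to 85% against the stated 91%. It reaches 85% for one arm only if a fifth of patients are listed. These figures assume that listing is spread evenly across arms and is unrelated to response.

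A reader might infer a biased comparison because listing is not a stratification factor. The documents do not support that. Under blinded randomization the rule falls on all arms alike. It shrinks the difference, and a chance imbalance is sampling variation. The error is conservative.

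Nor does it reach the US primary endpoint, since the pruritus rule names transplantation and not listing. The surgical endpoint is mainly descriptive and outside the multiplicity control, so there the harm is to interpretation. The text should be reconciled before analysis; the design does not need to change.

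**What to change.** Reconcile exclusion 9 with 9.1.2, 11.2.2.2 and 11.2.2.5 by adding a sentence to each of the last three: listing for transplant counts as rescue, non-response or a surgical event only when the patient is newly listed after the first dose. State that patients already listed at entry are classified by their Week 22/24 s-BA under the same responder definition as everyone else.

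Record listing status and its date at Visit 1 with the medical and surgical history. The history review already scheduled at Visit 3 can update it, so that old and new listings can be told apart.

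The cost is three sentences and one eCRF item, with no added patients, visits or samples. The change concerns endpoint classification only and takes no position on which patients may enter.
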